18.1.2 Deaths and Serious Adverse Events

If applicable, a listing of deaths and other SAEs will be provided by subject.

18.1.3 Laboratory Data

Safety laboratory data for Part A will be analyzed by PRA Clinical Laboratory, while the safety laboratory data for Part B, C and D will be analyzed by Medpace.

Clinical laboratory data will be presented using units from the study data tabulation model (SDTM) Controlled Terminology.

All laboratory data (absolute values and derived changes from baseline) will be listed, including laboratory variables not listed in the protocol. A separate listing, including out-of-range values will also be provided. Normal ranges will be used directly from the clinical laboratory.

Descriptive statistics summarizing continuous laboratory results of clinical chemistry, hematology and coagulation (observed and derived changes from baseline) by treatment and scheduled time will be included.

Summary of clinically significant ab normalities using shift tables will be presented for safety laboratory tests. These tables will present shifts from baseline to all post-dose time points according to categories: Non-Clinically Significant vs Clinically Significant. It will only be prepared for parameters for which >25% of subjects have a clinically-significant shift from baseline.

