### 9.3.2 Safety Analyses

All safety analyses will be performed on the SAF.

Endpoint	Statistical Analysis Methods
Primary	Analysis of all safety data will be performed on the Safety Analysis Set (SAF) and will be presented by the treatment received. Adverse events will be coded using Medical Dictionary for Regulatory Authorities (MedDRA). The occurrence of adverse events (AEs), serious AEs (SAEs), and AEs of Special Interest will be summarized in terms of incidence, as well as in terms of total number of AEs. Analysis of AEs in terms of incidence by severity and by relatedness will also be provided. Prior and concomitant medications will be coded by the World Health Organization Drug Dictionary Enhanced and will be listed. Medical history will be listed by subject and coded using the MedDRA. Descriptive statistics and a summary of clinically significant abnormalities using shift tables will be presented for safety laboratory tests, vital signs, electrocardiogram (ECGs), and other laboratory parameters. For vital signs and ECGs, descriptive statistics at each visit and change from baseline at each visit will be provided. Physical examinations will be summarized as shift tables. Listings will also be provided for each type of safety data.
Secondary	Not applicable.
Exploratory	Not applicable.

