3.0 Introduction

This Statistical Analysis Plan (SAP) describes the statistical methods that will be used during the analysis and reporting of data collected under Momenta Pharmaceuticals, Inc. Protocol MOM-M254-001.

This SAP should be read in conjunction with the study protocol and electronic case report form (eCRF). This version of the plan has been developed using the protocol dated 24 April 2020 (including all amendments up to this protocol date).

An approved and signed SAP is a requirement for database lock. An approved SAP is also required for unblinding of the study treatments.

This SAP only covers the results that will be processed by the PRA Early Development Services (EDS) Biostatistics Department.

PRA EDS will perform the pharmacokinetic (PK), pharmacodynamic (PD) and safety and tolerability evaluation.

This SAP supersedes the statistical considerations identified in the protocol; where considerations are substantially different, they will be so identified. Any post-hoc or unplanned analyses, or significant changes from the planned analysis in this SAP performed to provide results for inclusion in the clinical study report (CSR) but not included in this SAP, will be clearly identified in Section 9.8.2 of the CSR. Changes to planned analyses do not require an updated SAP but should be included in the CSR, if significant.

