5.0 Study Objectives

5.1 Primary

Part A:

• To assess the safety and tolerability of a single ascending dose of intravenous administration of M254 in healthy volunteers

Part B:

 To assess the safety and tolerability of a single intravenous administration of M254 in immune thrombocytopenia (previously called idiopathic thrombocytopenic purpura; ITP) patients compared to 1000 mg/kg intravenous immunoglobulin (IVIg)

Part C:

- To assess the safety of a single intravenous administration of M254 compared to 1000 mg/kg of IVIg
- To characterize the PD of single intravenous administration of M254 compared to 1000 mg/kg Nlg

Part D:

• To assess the safety and tolerability of repeated intravenous administration of M254 in ITP patients

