5.1.1 Primary Endpoint

Part A:

 Incidence and severity of adverse events (AEs) following administration of M254 at single dose levels

• Clinically significant changes in clinical safety labs, vital signs, and electrocardiograms (ECGs) with M254 administration

Part B:

- Incidence and severity of AEs following administration of M254 at single dose levels and 1000 mg/kg IVlg
- Clinically significant changes in clinical safety labs, vital signs, and ECGs following M254 administration and 1000 mg/kg IVIg

Part C:

- Incidence and severity of AEs of M254 and 1000 mg/kg IVIg
- Clinically significant changes in clinical safety labs, vital signs, and ECGs following M254 administration and 1000 mg/kg IVIg
- Platelet response after M254 administration compared to IVIg

Part D:

- Incidence and severity of AEs with repeated administration of M254
- Clinically significant changes in clinical safety labs, vital signs, and ECGs with M254 administration

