7.0 Overview of Planned Analysis

7.1 Changes from Protocol

To align with published reports of platelet response, an additional requirement of 'an increase from baseline of $\geq 20 \times 109/L$ ' was added to the definition of a therapeutic platelet count.

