9.1.3 Descriptive Statistics

Unless otherwise indicated, continuous variables will be summarized with the following descriptive statistics: n (number of observations), (arithmetic) mean, standard deviation (SD), minimum (min) value, median, and maximum (max) value. For PK and PD data, nblq (number of observations below the limit of quantification), CV, geometric mean, and coefficient of variation of the geometric mean (geoCV) will be presented additionally. If the total number of subjects per treatment is lower than 3 then the only descriptive statistics presented will be arithmetic mean, minimum and maximum.

Categorical data will be summarized with frequencies and percentages. Percentages by categories will be based on the number of subjects exposed within a treatment.

For categorical data the categories will be presented in the tables exactly as they appear in the eCRF / Database.

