10.1 Safety Set

The safety set will consist of subjects who receive at least one dose of M254 or IVIg or placebo. This set will be used for the safety data summaries and baseline characteristic summaries.

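### SAP 18.1.3 to 18.1.5 print the clinically significant shift tables only above a 25% threshold that Protocol 9.3.2 lacks, that SAP 7.1 does not list, and whose level is undefined

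*SAP*

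**What the plan says.** Protocol 9.3.2 commits to the tables without condition: "a summary of clinically significant abnormalities using shift tables will be presented for safety laboratory tests, vital signs", and it goes on to name ECGs.

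SAP 18.1.3 (laboratory), 18.1.4 (vital signs) and 18.1.5 (ECG) each repeat that commitment, describe the table as baseline against all post-dose time points, and then close with the same restriction: "It will only be prepared for parameters for which >25% of subjects have a clinically-significant shift from baseline". Appendix 4 marks the corresponding outputs (Tables 14.3.3.5 to 14.3.3.7, 14.3.4.2 and 14.3.4.4) as conditional but does not restate the 25%.

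The endpoint is primary. SAP 5.1.1 lists "Clinically significant changes in clinical safety labs, vital signs, and ECGs with M254 administration" for Parts A and D, with parallel wording that adds IVIg for Parts B and C. A primary objective of Part C in SAP 5.1 is comparative: "To assess the safety of a single intravenous administration of M254 compared to 1000 mg/kg of IVIg".

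On departures from the protocol, SAP 3.0 says that "where considerations are substantially different, they will be so identified". SAP 7.1 has a single entry, which begins "To align with published reports of platelet response, an additional requirement of" and adds a minimum rise from baseline to the therapeutic platelet count. The 25% rule is not there.

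On the denominator, SAP 9.1.3 gives a general default, "Percentages by categories will be based on the number of subjects exposed within a treatment", and SAP 10.1 says of the safety set: "This set will be used for the safety data summaries and baseline characteristic summaries". Neither says which group must exceed 25% before a parameter qualifies.

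**The concern.** No formal hypothesis testing is planned, so description is the whole of the safety analysis. The shift table is the only planned output that counts clinically significant changes by parameter, by time point and by treatment. Making it conditional on a frequency above 25% is a change to the reporting of a primary endpoint. It carries no stated reason and is not declared where the SAP says such changes will be declared.

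The undefined level adds to this. The same data can produce a table or none, depending on whether the 25% is checked in a treatment column, a cohort, a part total or a pooled M254 group. Left open, that choice can be made after the data are seen. Part C is where it matters most, because its layout in SAP 9.5 sets M254, IVIg and their difference side by side.

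**Working it through.** The plan gives no derivation for 25%, so there is no figure to reproduce. The check is what the rule does under its possible readings.

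**Inputs.** Part A: 3 on active drug per dose, 18 on M254 and 7 on placebo in all. Part B: 4 planned cohorts of 2, so 8. Part C: 2 cohorts of 10, so 20. Part D: 15 to 34. (Protocol 4.1.1 to 4.1.6.)

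**Step 1: counts.** Strictly more than 25% of n requires floor(n/4) + 1 subjects. The largest count that gives no table is floor(n/4).

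| Group | n | Largest count without a table | Needed for a table |
|---|---|---|---|
| Part B cohort | 2 | 0 | 1 |
| Part A active dose | 3 | 0 | 1 |
| Part A pooled placebo | 7 | 1 | 2 |
| Part B total | 8 | 2 | 3 |
| Part C cohort | 10 | 2 | 3 |
| Part D, lower size | 15 | 3 | 4 |
| Part A M254 total | 18 | 4 | 5 |
| Part C total | 20 | 5 | 6 |
| Part D, upper size, pooled | 34 | 8 | 9 |

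Exact 95% intervals: 2 of 10 gives 2.5% to 55.6%; 5 of 20 gives 8.7% to 49.1%. A count below the threshold is therefore compatible with a true rate well above 25%.

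The rows are not interchangeable. Five of 20 goes untabulated only if the Part C total is what is tested. Five patients over two cohorts of 10 put at least 3 in one cohort (30%), so a cohort-level test would print the table.

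**Step 2: reading 1, each column tested separately.** P(table) = P(X ≥ floor(n/4) + 1), X binomial(n, p). The documents give no shift rate, so p = 10% and 20% are assumptions.

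- n = 10: 7.0% at p = 10%, 32% at p = 20%.
- n = 20: 1.1% at p = 10%, 20% at p = 20%.

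Under an at-least-one rule, 1 − (1 − p)^n, the figures are 65% and 89% for n = 10, and 88% and 99% for n = 20.

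**Step 3: reading 2, a parameter qualifies once any column in any part exceeds 25%.** One event among the 18 Part A subjects on M254 (groups of 3) or the 8 Part B patients in their M254 period (groups of 2) is enough. With 18 + 8 = 26 subjects and the same assumed rates:

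- p = 10%: 1 − 0.9^26 = 94%.
- p = 20%: 1 − 0.8^26 = 99.7%.

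These are lower bounds under this reading, since other columns can also trigger the table.

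**Step 4: comparison.** For the same parameter and assumed rates, the chance of a table runs from 1.1% to 32% under reading 1 (n = 10 or 20) and is 94% or more under reading 2. The wording restricts parameters, not columns, and Appendix 4 titles each table for Parts A to D together, so reading 2 cannot be excluded. SAP 9.1.3 ties percentages to treatment, so neither can reading 1.

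**The case against.** A reader might infer that clinically significant findings drop out of the report, so that 2 of 10 after M254 against 0 of 10 after IVIg would go unseen. The documents do not support that.

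- Protocol 8.3 sends clinically significant changes from screening to the adverse event page. Sections 8.3.6 and 10.3.1 make clinically significant laboratory, vital-sign and ECG abnormalities adverse events. SAP 18.1.1 tabulates treatment-emergent events by preferred term, part and treatment with no threshold. The example would normally appear there.
- All laboratory and vital-sign values and all ECG measurements with their abnormalities are listed, out-of-range laboratory values have their own listing, and descriptive statistics are unrestricted.
- The shift tables are not flagged for the interim reports. Those carry the adverse event tables and listings of clinically significant findings, so nothing interim changes. Dose-escalation reports lie outside the SAP (section 7.2).

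It can also be said that Protocol 9.3 is only a summary, that SAP 3.0 promises to flag only substantial differences, and that suppressing sparse tables in an exploratory study is a display choice.

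Most of this stands, and it limits the consequence. It does not remove the point. Adverse event tables count by preferred term, not by parameter and visit. Sections 8.3.6 and 10.3.1 exclude abnormalities associated with the underlying disease unless more severe than expected, so those can be missing from the adverse event counts. Protocol 8.3 compares with screening, while SAP 9.2.1 sets a baseline per period in Parts B to D. Out of range is not the same as clinically significant. And SAP 18.1.6 already prepares the physical examination shift table whenever abnormalities are reported, so a lower trigger is the SAP's own practice.

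**Conclusion.** The point holds in a limited form. The SAP makes the tabulation of a primary safety endpoint conditional on an unexplained frequency, does not declare this in section 7.1, and does not define the group to which the frequency applies. The loss is confined to the final report: the per-parameter, per-time-point count by treatment, including disease-associated abnormalities that are not adverse events. The underlying data are not lost.

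The size depends on the reading. Column by column, up to 2 of 10 in a Part C cohort, 5 of 20 in the Part C total or 8 of 34 in Part D could shift with no table. The rule never suppresses an event in a Part A active group of 3 or a Part B cohort of 2. If any column in any part can qualify a parameter, it seldom suppresses anything. It would be wrong to quote the low printing probabilities as a property of the plan: they are conditional on the column-by-column reading and on assumed rates of 10% to 20%, taken as equal and independent across subjects. Importance lies between a minor clarification and a change that should be made.

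**What to change.** Delete the 25% sentence from SAP 18.1.3, 18.1.4 and 18.1.5. Produce the shift table, with n and % by part and treatment, for every parameter with at least one clinically significant post-dose shift in any subject, and state in the report that no other parameter had any. This is the kind of trigger SAP 18.1.6 already uses. Because it is still a display rule that Protocol 9.3.2 does not contain, record it in SAP 7.1.

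If the sponsor prefers to keep a percentage, the minimum is to list it in SAP 7.1 with a reason and to name the group in which it is tested.

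The cost is SAP wording and a few more, mostly sparse, tables within outputs already numbered in Appendix 4. No new data are needed.

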18.1.4 Vital Signs

Vital signs data (absolute values and changes from baseline) will be listed and summarized descriptively.

Summary of clinically significant abnormalities using shift tables will be presented for vital signs. These tables will present shifts from baseline to all post-dose time points according to categories: Non-Clinically Significant vs Clinically Significant. It will only be prepared for parameters for which >25% of subjects have a clinically-significant shift from baseline.

18.1.5 Electrocardiograms

The observed measurements for all ECG parameters and the corresponding abnormalities will be listed for all timepoints. The means of triplicate measurements for continuous parameters and the change from baseline of the mean triplicate measurements at each scheduled timepoint will be listed by subject.

Descriptive statistics will be provided to summarize mean ECG parameters (observed and changes from baseline) by part, treatment and scheduled time.

Summary of clinically significant abnormalities using shift tables will be presented for ECGs. These tables will present shifts from baseline to all post-dose time points according to categories: Non-Clinically Significant vs Clinically Significant. It will only be prepared for parameters for which >25% of subjects have a clinically-significant shift from baseline.

18.1.6 Physical Examination

The findings (abnormalities) at screening and changes from/new findings since screening will be listed. If abnormalities in the physical examinations are reported, physical examinations will be summarized as shift tables (categories: Normal vs Abnormal).

Appendix 1: Glossary of Abbreviations

Glossary of Abbreviation	ons:
AE	Adverse event
ADaM	Analysis data model
ANOVA	Analysis of variance
BMI	Body mass index
BQL	Below the quantifiable limit
CDISC	Clinical Data Interchange Standard Consortium
CI	Confidence interval
CSR	Clinical study report
CV	Coefficient of variation
DBP	Diastolic blood pressure
ECG	Electrocardiogram
eCRF	Electronic case report form
EDS	Early Development Services
FAS	Full Analysis Set
ICH	The International Council for Harmonization of Technical Requirements for Pharmaceuticals for Human Use
lgG	Immunoglobulin G
LLOQ	Lower limit of quantification
max	Maximum value
MedDRA	Medical Dictionary for Regulatory Activities
min	Minimum value
PD	Pharmacodynamic
РК	Pharmacokinetic
PP	PerProtocol
PRA	PRA Health Sciences
QA'd	Quality assured
QC('d)	Quality control(led)
SAP	Statistical analysis plan
SAE	Serious adverse event
SBP	Systolic blood pressure
SD	Standard deviation
SDTM	Study data tabulation model
TEAE	Treatment-emergent adverse event

TFL(s)	Tables, figures and listings
WNL	WinNonlin

Appendix 2: Schedule of Assessments

Table 1-1.	Part A Schedule of Activ	vities (Netherlands only)
------------	--------------------------	---------------------------

Day	-28 to -2	-1	1	1	1	1	1	1	1	1	1	1	2	3	4	5	8 ±1	10 ⁿ ±1	12 ⁿ ±1	15 ±1	18 ⁿ ±1	22 ±1	29 ±2
	Screening	Pre-infusion	Infusion									Post-i	nfusio	1. 1.									Follow-up
Procedure ^a Hour		0	0	0 (end of infusion)	0.08 (5 min)	0.25	0.5	1	2	4	8	12	0	0	0	0	0	0	0	0	0	0	0
Unit Admit		x									a												
Informed Consent	x																			92 92			
Demographics	x																						
Prior/Concomitant Medications ^e	x	x	x	x	x	x	x	x	x	x	x	x	x	x	x	x	x	x	x	x	x	x	x
AE Assessment ^e	x	X	X	X	X	x	X	x	X	x	x	x	x	x	x	X	X	x	X	х	X	x	x
Medical History	x																						
Inclusion/Exclusion Criteria ^b	x	x																					
Physical Examination	x	Xp								x													Xp
Drug Screening	x																						
Body Weight	x	x							1	×*.	Ĩ							-					x
Height and Body Mass Index	x																						
Vital signs ^e	x	X	X	X°	x	x	X	X	X	x	X	X	X	x	x	X	X			x		x	X
12-lead ECG	x	X		X°					X	X	X	x	X										X
Safety Labs ^f	Xf	х	X								a - :	X	X	х	a	x	х			х	a s	x	X

	-						-					-								-		·	+
Day	-28 to -2	-1	1	1	1	1	1	1	1	1	1	1	2	3	4	5	8 ±1	10 ⁿ ±1	12 ⁿ ±1	15 ±1	18 ⁿ ±1	22 ±1	29 ±2
	Screening	Pre-infusion	Infusion						1 99	•		Post-	infusio	n									Follow-up
Procedure ^a Hour		0	0	0 (end of infusion)	0.08 (5 min)	0.25	0.5	1	2	4	8	12	0	0	0	0	0	0	0	0	0	0	0
Serology: HBsAg, anti-HCV, anti-HIV 1 and 2	x																						
Total IgG ^h		x	x	х	10 S	X	х	9-5.	х	x		x	х	x	3 2	x	x		3	X	A	х	х
Blood Samples for PK ^{h, i}		2	Xq	X	x	x	X	х	X	x	x	x	X	x	X	X	x			x		x	x
Blood Samples for Biomarkers		x						25	12	2. 2		Ş.	x	85 B	2		x						8.5
Urinalysis	x	X	x	\$				5				X	x	x		x	x			x		x	x
Pregnancy Test ^g	x	x	2¢	8	10. ÷			Č.	8			*		K - 6			3				, č	0.	x
Telemetry (set on alarm) ^d		92	x	х				8 :	0				8	8: 								8	
M254 IV Infusion ^j		de L	X (start)	X ^k (end)					10 			2.										2	
Infusion Reaction ¹		X	x	X		X	X	x	x	x	X	X	X	x	x	X							
Unit Discharge																X							
Discharge from Study		83. 	8	8				λ.	ð.	a 8				12. J		2					A	2	Xm

Table 1-1. Part A Schedule of Activities (Netherlands only)

AE = adverse event; ECG = electrocardiogram; HBsAg = hepatitis B surface antigen; HCV = hepatitis C virus; HIV = human immunodeficiency virus; IgG = immunoglobulin G; IV = intravenous; PK = pharmacokinetics.

Page 31 of 52

Statistical Analysis Plan MMT102EC-170091 Protocol: MOM-M254-001 Version 2 Date: 14-Jul-2021

- ^a Procedures should occur in the order presented above from top to bottom if more than 1 procedure occurs at the same nominal time Urine sampling or anything with a specific footnote may be done out of order.
- ^c Inclusion/exclusion criteria does not need to be redone for subsequent dose of IVIg, but follow other pre-infusion assessments.
- ^d Vital signs includes tympanic body temperature, supine (after 5 minutes) blood pressure, pulse rate, and respiratory rate. Vital signs will be assessed every 30 minutes during an infusion with a window +3 minutes. For infusions <35 minutes, vital signs assessments may occur just after starting the infusion and just prior to the end of the infusion. Refer to Footnote O for exception.
- e Telemetry should start at or before beginning of infusion and stop at or after end of infusion.
- f Concomitant Medications and AEs will be assessed throughout the infusion and the study. Subjects will be queried and observed for AEs daily during the confinement period, then at each subsequent clinic visit.
- g Safety labs will include complete blood count (CBC), hematology, serum chemistry, coagulation, and coagulation screening lab (at screening only) (see Table 10-1).
- ^h Women of childbearing potential, only. Urine test on Day -1; serum test during Screening and on Day 29.
- ⁱ Samples should be analyzed in a blinded fashion in Part A see Part A lab manual for additional details.
- j Samples drawn 15 minutes after in supine position at in-house visits. For ambulatory visits, samples drawn 15 minutes after sitting.
- ^k Duration of infusion is based on dosing instructions (details provided in the pharmacy manual). Patients will be required to drink 2 glasses of liquid in the morning before the start of infusion. Just before infusion, patients will be provided the opportunity to urinate.
- If infusion duration is <20 minutes, end of infusion activities may be scheduled as logistically feasible with the PK sample drawn from 1 minute before the end of infusion to 2 minutes after the end of infusion. For infusion durations ≥20 minutes, activities should occur in the order of the table (top to bottom) unless a footnote indicates otherwise.

- ^m Subjects will assessed for 2 types of infusion reactions: 1) cutaneous infusion reaction 2) systemic reactions. For either types of infusion reactions and AE must be recorded. In the event of systemic reactions, a sample of blood will be drawn to measure histamine, anaphylatoxin (C5a), IgE, and tryptase and will be compared with the baseline sample drawn prior to the first dose of study drug.
- ⁿ Discharge from study after final study period unless further follow-up of open AEs is deemed necessary by the Investigator.
- ^o Follow-up may be conducted by telephone for these visits
- ^p ECG and vital signs assessments required at the end of the infusion may be initiated 15 minutes prior to the end of infusion
- ^q These should be conducted as abbreviated physical exams
- ¹ PK sample is required prior to the start of infusion (on the day of the infusion).

 Table 1-2.
 Part B Schedule of Activities (USA sites included)

(Schedule of Activities below is repeated when the patient receives their second infusion, which will be IVIg)

Day	-28 to -2	-1 ⁿ	1 ⁿ	1	1	1	1	1	2	3 ^b	4 ^b	5 ^b	8±1 ^b	10 ±3	12 ±3 ^b	15 ±3 ^b	18 ±3 ^b	22 ±3 ^b	29 ±3 ⁿ
	Screening	Pre-infusion	Infusion							Post	-infusio	1							Follow-up
Procedure ^a Hour		0	0	0 (end of infusion)	0.25	0.5	2	4	0	0	0	0	0	0	0	0	0	0	0
Unit Admit			X															0	
Informed Consent	x						с с												
Demographics	X															83 69			
Prior/Concomitant Medications ^f	x	X	x	x	x	x	x	X	x	x	х	X	x	x	x	х	x	X	x
AE Assessment ^f	x	Х	X	x	x x x	x
ITP-BAT		Х																	Xs
Medical History	x																		
Inclusion/Exclusion Criteria	x											-							
Physical Examination	x	Xu																	Xu
Drug Screening	x															-			
Body Weight ^c	x	X					a a					ŝ.							x
Height and Body Mass Index	x											6				82			
Vital Signs ^d	x	X	X	Xt	X	Х	X	X	X	х	X	Х	X	X	х	Х	X	X	X
12-lead ECG	x	X		Xt		Х	X	X				e e				82 82			х
Safety Labs ^g	Xg	Х						X	X		х		X			х		Х	х

Table 1-2. Part B Schedule of Activities (USA sites included)

(Schedule of Activities below is repeated when the patient receives their second infusion, which will be IVIg)

Day	-28 to -2	-1 ⁿ	1 ⁿ	1	1	1	1	1	2	3 ^b	4 ^b	5 ^b	8±1 ^b	10 ±3	12 ±3 ^b	15 ±3 ^b	18 ±3 ^b	22 ±3 ^b	29 ±3 ⁿ
	Screening	Pre-infusion	Infusion							Post	-infusio	n							Follow-up
Procedure ^a Hour	12121	0	0	0 (end of infusion)	0.25	0.5	2	4	0	0	0	0	0	0	0	0	0	0	0
Serology: HBsAg, anti-HCV, anti-HIV 1 and 2	x								0										
Platelet Count ^h	х	х						X	X	х	X	X	х	X	x	Х	х	х	x
Blood type, if unknown	х																		
Platelet Autoantibodies, if unknown	x																		
Total IgG ^j	х	X		х	X	x	X	X	X	х	X	X	X			х		x	X
Blood Samples for PK ^r			Xv	X	x	x	X	x	X	x	x	x	x			х		х	x
Blood Samples for Biomarkers and ADA ^w		x		6				у. 	x				x						x
Urinalysis	х	x							X				x			х		х	x
Pregnancy Test ⁱ	x	x		2.					S.										х
Telemetry (set on alarm) ^e			x	8 8					2						° °				
M254 or IVIg IV Infusion ^k			X (start)	X ^l (end)															Xq
Infusion Reaction ^m		x	x	X	x	x	X	X	X										x
Unit Discharge	a k			5 D	6			X°	84	a a	2				a k				

Table 1-2. Part B Schedule of Activities (USA sites included)

(Schedule of Activities below is repeated when the patient receives their second infusion, which will be IVIg)

	Day	-28 to -2	- 1 ⁿ	1 ⁿ	1	1	1	1	1	2	3 ^b	4 ^b	5 ^b	8±1 ^b	10 ±3	12 ±3 ^b	15 ±3 ^b	18 ±3 ^b	22 ±3 ^b	29 ±3 ⁿ
		Screening	Pre-infusion	Infusion							Post	-infusio	1							Follow-up
Procedure ^a	Hour		0	0	0 (end of infusion)	0.25	0.5	2	4	0	0	0	0	0	0	0	0	0	0	0
Discharge from	n Study				8: 				20		22	с с	3							Xp

ADA = anti-drug antibody; AE = adverse event; ECG = electrocardiogram; HBsAg = hepatitis B surface antigen; HCV = hepatitis C virus; HIV = human immunodeficiency virus; IgG = immunoglobulin G; ITP-BAT = immune thrombocytopenic purpura bleeding assessment tool; IV = intravenous; PK = pharmacokinetics.

- ^a Procedures should occur in the order presented above from top to bottom if more than 1 procedure occurs at the same nominal time. Urine sampling or anything with a specific footnote may be done out of order.
- ^b Only visits required to be at the study site are screening, infusions, the day after infusion, Day 10 after M254 infusion (as this is last safety visit prior to dose escalation decision), and Day 29, all others can be done by visiting nurse if patient prefers this option. Visit windows of ±1 day should be used whenever possible; ±3 day windows shouldonly be used when required due to clinical site closures (eg, for holidays or COVID-19-related limited schedules). When visit windows overlap, they must not be combined into a single actual day. Note: the first patient in the 500 mg/kg cohort must be seen in clinic at the Day 15 visit as there will be a 14-day safety monitoring period between enrollment of the first and second patients in the 500 mg/kg cohort.
- ^c Screening weight will be used to determine eligibility and dosing, and will allow up to 1 month for weight variability.
- ^d Vital signs includes body temperature, supine (after 5 minutes) blood pressure, pulse rate, and respiratory rate. Vital signs will be assessed every 30 minutes during an infusion. For infusions <35 minutes, vital signs assessments may occur just after starting the infusion and just prior to the end of the infusion. Refer to Footnote t for exception.
- e Telemetry should start at or before beginning of the M254 infusion and stop at or after end of infusion. Telemetry does not need to be performed during the IVIg infusion.
- f Concomitant Medications and AEs will be assessed throughout the infusion and the study. Subjects will be queried and observed for AEs daily during the confinement period, then at each subsequent clinic visit. Should there be a bleeding event reported by the patient or observed by the physician during examination, the ITP-BAT must be completed, see ITP-BAT in Appendix 6, as well as an AE form.
- g Safety labs will include complete blood count (CBC), serum chemistry, coagulation, and coagulation screening lab (at screening only) (see Table 10-1). All safety labs will be assessed by the Central lab except for platelet counts, which should be done locally at all the visits where they are scheduled. In case of an AE that requires additional sampling and the Investigator needs to review the results to determine patient care, additional safety labs can be assessed by the local lab.

Statistical Analysis Plan MMT102EC-170091 Protocol: MOM-M254-001 Version 2 Date: 14-Jul-2021

- ^h The platelet measurement for eligibility must be taken within 96 hours of start of infusion. Platelet sample may be combined with safety labs if sample is taken at the same time. All scheduled platelet measurements must be sent to the central lab. If there is insufficient time to review the central lab results an additional local lab sample may be obtained in order to assess eligibility for infusion.
- ¹ Women of childbearing potential, only. Urine test on Day -1 for Day 1 prior to infusion; serum test during Screening and on Day 29. Central lab should assess serum sample collected at screening and on Day 29, but the local lab can assess the urine test on Day -1/Day 1 prior to the infusion.
- ^j Duplicate samples for IgG should not be drawn if sample was already taken with safety labs collection.
- k Duration of infusion is based on dosing instructions (details provided in the pharmacy manual). Patients will be required to drink 2 glasses of liquid in the morning before the start of infusion. Just before infusion, patients will be provided the opportunity to urinate. Patients receiving M254 or IVIg can be discharged 4 hours post-infusion.
- I If infusion duration is <20 minutes, end of infusion activities may be scheduled as logistically feasible with the PK sample drawn from 1 minute before the end of infusion to 2 minutes after the end of infusion. For infusion durations ≥20 minutes, activities should occur in the order of the table (top to bottom) unless a footnote indicates otherwise.

- ^m All systemic infusion reactions and associated AEs will be graded using Common Terminology Criteria for Adverse Events (CTCAE)
- ⁿ Patients with ITP may be admitted to the unit the morning of Day 1so any procedure specified on Day -1 can occur on Day 1, but all results must be back before infusion begins. Likewise, any pre-infusion assessment specified on Day 1 can occur on Day -1 and does not need to be duplicated.
- ^o Study staff should follow-up with the patient approximately 12 hours post-discharge for safety via phone call.
- ^p Discharge from study after final study period unless further follow-up of open AEs is deemed necessary by the Investigator.
- ^q IVIg infusion will occur on this day if patient's platelet count meets criteria, and then the Schedule of Activities should be followed starting at Day 1. For Period 2, Day 1, any assessments completed on the same date for Period 1 follow-up do not need to be duplicated.
- ¹ Blood sample for PK is required during the M254 treatment period only. It is NOT needed for the IVIg treatment period.
- ⁵ ITP-BAT to be completed separately at Day 1 and 29 of each period (M254- and IVIg-treatment). Only 1 ITP-BAT assessment is needed if Day 29 of the first period is the same as Day 1 of the second period.
- t ECG and vital signs assessments required at the end of the infusion may be initiated 15 minutes prior to the end of infusion
- ^u These should be conducted as abbreviated physical exams
- v PK sample is required prior to the start of infusion (on the day of the infusion).
- W Biomarker samples are collected at pre-infusion, Day 2, and Day 8; ADA samples are collected at pre-infusion and Day 29 follow-up. Please refer to the lab manual for specific instructions.

Table 1-3. Part C Schedule of Activities (USA sites included)

(Schedule of Activities below is repeated when the patient receives their second infusion, which will be either M254 or IVIg)

Day	-28 to -2	-1 ^m	1 ^m	1	1	1	1	1	2	3 ^b	4 ^b	5 ^b	8±1 ^b	10 ±3 ^b	12 ±3 ^b	15 ±3 ^b	18 ±3 ^b	22 ±3 ^b	29 ±3 ⁿ
	Screening	Pre-infusion	Infusion					5		Post	-infusio	n ,		2					Follow-up
Procedure ^a Hour	34146	0	0	0 (end of infusion)	0.25	0.5	2	4	0	0	0	0	0	0	0	0	0	0	0
Informed Consent	x							č, č,											
Demographics	x				¢.	65		0 0							60 	e.s.			
Prior/Concomitant Medications ^e	x	x	x	x	x	x	x	x	x	x	x	x	x	x	x	x	x	X	x
AE Assessment ^e	x	х	x	X	х	X	X	X	X	x	х	x	х	х	X	X	X	X	х
ITP-BAT	8 8	х				i.e	8	a a									a a		Xr
Medical History	X					8 9	63. 52												
Inclusion/Exclusion Criteria	x																		
Physical Examination	X	Xt				8 8	63. 52									63 69			Xt
Drug Screening	X					×.	12	a 10								8	a 10		
Body Weight ^e	X	х														2			X
Height and Body Mass Index	x					-										~			
Vital Signs ^d	X	х	x	Xs	X	x	X	X	x	X	X	x	X	X	X	Х	x	x	X
12-lead ECG	x	x		Xs		X	X	X											х
Safety Labs ^f	Xg	X			×.		5	X	X		х		х		ò.	Х	о 	X	х

Table 1-3. Part C Schedule of Activities (USA sites included)

(Schedule of Activities below is repeated when the patient receives their second infusion, which will be either M254 or IVIg)

Day	-28 to -2	-1 ^m	1 ^m	1	1	1	1	1	2	3 ^b	4 ^b	5 ^b	8±1 ^b	10 ±3 ^b	12 ±3 ^b	15 ±3 ^b	18 ±3 ^b	22 ±3 ^b	29 ±3 ⁿ
	Screening	Pre-infusion	Infusion		- 25					Post	-infusio	n					- 20		Follow-up
Procedure ^a Hour	-	0	0	0 (end of infusion)	0.25	0.5	2	4	0	0	0	0	0	0	0	0	0	0	0
Serology: HBsAg, anti-HCV, anti-HIV 1 and 2	x																		
Platelet Count ^g	х	X	8 8					X	х	х	х	х	X	X	х	Х	X	X	X
Bloodtype, if unknown	X				-						8	8: 0	62 62						
Platelet Autoantibodies, if unknown	x																		
Total IgG ⁱ	Х	Х	X	X	Х			Х	х	6 2		x	х			X		X	х
Blood Samples for PK ^q			Xu	x	х			X	х			x	X			Х		X	х
Blood Samples for Biomarkers and ADA ^v		x							x	2			x						x
Urinalysis	Х	X	s3					X	X			8	Х			Х		X	Х
Pregnancy Test ^h	х	X										~							х
M254 or IVIg IV Infusion ^j		7	X (start)	X ^k (end)															Xp
Infusion Reaction ¹		х	х	X	Х	Х	х	X	Х	0	×.	~							х
Unit Discharge								X ⁿ											
Discharge from Study		2.									ю.								X°

Statistical Analysis Plan MMT102EC-170091 Protocol: MOM-M254-001 Version 2 Date: 14-Jul-2021

ADA = anti-drug antibody; AE = adverse event; ECG = electrocardiogram; HBsAg = hepatitis B surface antigen; HCV = hepatitis C virus; HIV = human immunodeficiency virus; IgG = immunoglobulin G; ITP-BAT = immune thrombocytopenic purpura bleeding assessment tool; IV = intravenous; PK = pharmacokinetics.

- ^a Procedures should occur in the order presented above from top to bottom if more than 1 procedure occurs at the same nominal time. Urine sampling or anything with a specific footnote may be done out of order.
- ^b Only visits required to be at the study site are screening, infusions, the day after an infusion, and Day 29, all others can be done by visiting nurse if patient prefers this option. Visit windows of ±1 day should be used whenever possible; ±3 day windows should only be used when required due to clinical site closures (eg, for holidays or COVID-19related limited schedules). When visit windows overlap, they must not be combined into a single actual day.
- ^c Screening weight will be used to determine eligibility and dosing, and will allow up to 1 month for weight variability.
- ^d Vital signs includes body temperature, supine (after 5 minutes) blood pressure, pulse rate, and respiratory rate. Vital signs will be assessed every 30 minutes during an infusion. For infusions <35 minutes, vital signs assessments may occur just after starting the infusion and just prior to the end of the infusion. Refer to Footnote s for exception.

- ^e Concomitant Medications and AEs will be assessed throughout the infusion and the study. Subjects will be queried and observed for AEs daily during the confinement period, then at each subsequent clinic visit. Should there be a bleeding event reported by the patient or observed by the physician during examination, the ITP-BAT must be completed, see ITP-BAT in Appendix 6, as well as an AE form.
- f Safety labs will include complete blood count (CBC), serum chemistry, coagulation, and coagulation screening lab (at screening only) (see Table 10-1). All safety labs will be assessed by the central lab, except for platelet counts, which should be done locally at all the visits where they are scheduled. In case of an AE that requires additional sampling and the Investigator needs to review the results to determine patient care additional safety labs can be assessed by the local lab.
